7.3 Confidentiality and data protection

This study fully complies with Spanish and European data protection regulations, including Organic Law 3/2018, of December 5, on the Protection of Personal Data and guarantee of digital rights, as well as Regulation (EU) 2016/679 of the European Parliament and of the Council of 27 April 2016 on the protection of natural persons with regard to the processing of personal data and the free circulation of such data.

Origin of data: Data will be obtained both directly from patients through questionnaires and evaluations, and from their medical records to collect demographic and clinical data.

Consent for data processing: Informed consent will be obtained from all patients for the processing of their data. Additionally, we will keep this data pseudonymized to protect the identity of patients.

External promoter with access to data: There is no external promoter with access to data. Only the principal investigators of the study will have access to the full data.

Collaboration with companies: We work in collaboration with the company Reality Telling, however, the results of the study will only be shared with them after being analyzed and without personal data that allows the participants to be identified. In no case will raw data be shared directly from participants or any personal data that may identify them.

Data storage location and IT tools: Data will be stored securely within the BSA intranet. The computer tools we use to manage and analyze data are secure and have been approved by the Information Systems Department.

Security measures: We have implemented rigorous security measures, including access codes and passwords, to ensure that only members of the research team have access to the data.

International Data Transfers: No international data transfers are planned.

High-risk treatments: High-risk treatments are not foreseen, such as data profiling techniques, automated decision making, artificial intelligence, data exploitation with Big Data technologies, biometrics or geolocation systems. All data will be used exclusively for the purposes of this study and will be handled in accordance with applicable data protection regulations..

8. MANAGEMENT AND COMMUNICATION OF ADVERSE REACTIONS

As this study uses virtual reality in cognitive stimulation for patients with cognitive impairment and does not involve the use of medications, the management and communication of adverse drug reactions is not applicable in this context.

However, any adverse side effects associated with the use of virtual reality technology, such as dizziness, nausea or disorientation, will be carefully recorded and monitored by the research team. Healthcare professionals are trained to handle these incidents and will provide necessary care to study participants should these adverse effects occur.

The research team agrees to inform the collaborating company, Reality Telling, about any incident that occurs during the study, respecting the confidentiality of the participants. In the event of a serious adverse reaction, the research team will take necessary steps to ensure the safety of the participant and determine whether their participation in the study needs to be adjusted or discontinued.

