5.2 Design

This study will be prospective and non-randomized in design. Patients will be selected from among those who already attend cognitive rehabilitation sessions at the CSSC Day Hospital. There will be no control group in this pilot study, as the primary objective is to evaluate the usability and acceptability of the intervention.

Experimental group: This group will be made up of 20 patients who attend cognitive rehabilitation sessions at the CSSC Day Hospital. These patients will participate in 8 cognitive rehabilitation sessions that will incorporate the VR experiences developed for this study.

Intervention

Sessions:

The 8 sessions will be held two days a week, at the time when the included participants have an appointment for the conventional cognitive rehabilitation program at the CSSC Day Hospital.

Equipment and Technology:

We use Oculus Quest 2 glasses and their hand tracking technology, which allows for a more immersive and less complicated experience for participants, especially those with MCI.

Developed Virtual Reality Experiences:

A) Interactive Cognitive Stimulation Exercises (Declarative Memory, Executive Functions):

Developed jointly by the BSA VR and Reality Telling teams, following the researchers' guidelines, three types of sequential interactive exercises have been created:

Step 1- Make a Purchase at the Supermarket:

- Scenario: Virtual supermarket.
- Avatar: An animated avatar greets the participant and provides instructions.
- Objective: Select ingredients to make a potato omelet or gazpacho.
- Interaction: Participants use hand tracking technology to grab products and place them in a virtual cart.
- Feedback: A success or error audio is emitted based on the product selection.

Step 2- Pay for the Purchase:

- Scenario: Checkout area of the virtual supermarket.
- Avatar: An animated avatar greets the participant and provides instructions.
- Objective: Pay the exact amount for the selected products.
- Interaction: Select 3D models of bills and coins to reach the correct sum.
- Feedback: An avatar and audio provide confirmation or correction.

Step 3- Sort the Recipe Steps:

- Scenario: Virtual kitchen.
- Avatar: An animated avatar greets the participant and provides instructions.
- Objective: Sort photos of the recipe steps.
- Interaction: Drag and drop photos into a numbered panel.
- Feedback: Confirmation of the avatar.

Scenario details:

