5.6 Sample size

The sample size for this pilot study has been established at 20 patients. This decision is based on several factors:

Preliminary nature of the study: As this is a pilot study, the primary objective is to evaluate the usability and acceptability of the virtual reality intervention, rather than to demonstrate effectiveness. Pilot studies typically have smaller sample sizes than full studies.

Resources and capacity: The capacity of the El Carme Socio-Health Center in Badalona and the available resources (both in terms of staff and virtual reality equipment) also influence the sample size. Ensuring that each participant can receive appropriate care and support is

critical to accurate data collection and a positive patient experience.

Patient variability: Although the sample size is small, it is expected to reflect the diversity of the patient population in terms of severity of cognitive impairment, gender, age, etc. This diversity may provide a deeper understanding of how different types of patients may interact with virtual reality technology.

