7. PROTECTION OF PERSONS UNDER INVESTIGATION

7.1 Benefit-risk evaluation for research subjects

This interventional study uses virtual reality (VR) for cognitive stimulation of patients with cognitive impairment. The following potential risks and benefits to participants have been identified, along with specific mitigation strategies for the identified risks.

Risks and Mitigation Strategies:

1- Side effects of VR: Some patients may experience dizziness or disorientation with VR. To mitigate this risk, static or smooth motion VR experiences will be designed, and the technology will be introduced gradually. Side effects will be carefully monitored, especially in patients with conditions that may increase risk.

2- Patient acceptance: Since VR is a relatively new technology, it can be intimidating for some patients. To overcome this barrier, the potential benefits of VR will be effectively communicated and patient concerns will be proactively managed. Engagement with healthcare personnel during the process can improve patient acceptance and adherence.

3- Technical problems: Like any technology, VR can face technical problems such as hardware or software failures, or Internet connectivity problems. To mitigate this risk, backup equipment will be available and appropriate training will be provided to healthcare personnel to handle VR equipment. Fast and efficient technical support will also be guaranteed to resolve any issues that may arise.

4- Technical problems: Like any technology, VR can face technical problems such as hardware or software failures, or Internet connectivity problems. To mitigate this risk, backup equipment will be available and appropriate training will be provided to healthcare personnel to handle VR equipment. Fast and efficient technical support will also be guaranteed to resolve any issues that may arise.

5- Exclusion of certain patients: Some patients may not be able to participate due to severe cognitive impairment, dizziness, certain visual impairments or other health conditions, which could potentially lead to feelings of exclusion or frustration. To mitigate this risk, communication with patients about the limitations of who can participate in the study will be clear, explaining health and safety reasons. For those patients who are unable to participate, other alternative activities or interventions will be explored.

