6- Physical safety: There is a risk of patients tripping or falling while using VR due to spatial disorientation. To mitigate this risk, patients will be seated during VR sessions and will be

closely supervised by healthcare personnel to ensure their safety. Additionally, the area around the patient will be free of obstacles.

7- Withdrawal effect: If the VR tool is withdrawn after the conclusion of the study, the patients who participated may show less interest in continuing with the conventional cognitive stimulation program. To mitigate this risk, if the results of the study are positive and show significant benefits for patients, a commitment will be made to keep this tool in use within the cognitive stimulation program.

Benefits

1- Cognitive stimulation: VR offers an interactive and attractive medium for cognitive stimulation, which can be more motivating and attractive for patients than traditional therapies.

2- Improved emotional well-being: Patients may experience an improvement in their emotional well-being when participating in immersive VR experiences, especially if the sessions are designed to be enjoyable and fun.

3- Contribution to research: Patients will participate in a study that may contribute to improving the understanding and treatment of cognitive impairment.

To ensure the safety and comfort of participants, healthcare personnel will receive extensive training in the use of VR. All necessary precautions will be taken to minimize risks and participants will be closely monitored for any side effects. It is hoped that participation in the study can have a positive impact on the cognition and emotional well-being of the participants, and that it contributes to research in this field.

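### Section 8 ties the recording of harms to a link with VR, with no all-cause rule and no fixed question, and Annex 7 closes only part of the gap

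*Combined protocol and SAP*

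**What the plan says.** Section 8 sets the only explicit duty to record harms: "any adverse side effects associated with the use of virtual reality technology, such as dizziness, nausea or disorientation, will be carefully recorded". The research team does the recording. The section does not say how a link with VR is decided, what happens to events not thought to be linked, or when and how patients are asked. It also promises to inform the collaborating company "about any incident that occurs during the study".

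Section 7.1 deals with supervision. Under the side effects of VR it states: "Side effects will be carefully monitored, especially in patients with conditions that may increase risk". Its closing paragraph applies to everyone: "participants will be closely monitored for any side effects". Under physical safety it names a further harm: "There is a risk of patients tripping or falling while using VR due to spatial disorientation".

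Annex 7, the patient questionnaire, has headset items on dizziness, headache, visual discomfort, tired arms and fingers, and having to stop, plus a comments field. Sections 5.4.1 and 5.5 place the patient questionnaires at the eighth session. Section 6.1 says acceptability and usability questionnaires are completed after every session.

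Side effects do not appear among the variables in 5.4, in the visit table in 5.5 or in the analyses in 5.7. On design, 5.2 states: "There will be no control group in this pilot study". On size, 5.6 states: "The sample size for this pilot study has been established at 20 patients".

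**The concern.** If an event must be associated with VR to fall under the recording duty, some judgement of cause comes before the record. A headache that evening, a fall at home the next day or a spell of confusion in a patient aged 60 or over has many possible explanations. If nobody connects it with the headset, section 8 does not require a record. If nobody asks, it may never be mentioned.

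A control group would show the background rate of such events and might reveal thin recording. This study has none, so the number of patients with events is the whole of the safety evidence. A report of few or no side effects could then reflect good tolerability or incomplete recording, and a reader could not tell which. Tolerability bears on the acceptability that the study sets out to measure, and on the undertaking in 7.1 to keep the tool in use if results are positive.

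**Working it through.** The plan gives no event rate, detection rate or safety precision target, so there is no figure of its own to reproduce. The check has three parts.

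**1. What each route covers**

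| Harm | Section 8 | Annex 7 |
|---|---|---|
| Dizziness | named, if associated with VR | asked directly |
| Headache, visual discomfort, tired arms or fingers, having to stop | not named; covered if associated with VR | asked directly |
| Nausea | named, if associated with VR | no item |
| Disorientation | named, if associated with VR | no item |
| Falls (risk named in 7.1) | not named; covered if associated with VR | no item |
| Events between sessions | no question | no item |

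Two of the three effects that section 8 names, and the fall risk in 7.1, therefore depend on the section 8 route alone.

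Timing also matters. Eight sessions at two per week (5.2) last 8 / 2 = 4 weeks. If Annex 7 is given only after session 8, it asks patients with cognitive impairment to look back over about four weeks. It also misses anyone who left earlier, including those withdrawn for health problems under 5.3. If it is given after each session, as 6.1 says, both weaknesses shrink.

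**2. Illustration of size**

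Inputs: n = 20 (5.6). The true share of patients with an event, p, and the share of those cases that get recorded, f, are assumptions. The model covers the section 8 route alone, before any capture by Annex 7.

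Expected recorded cases = 20 × p × f. Chance of recording none = (1 − p × f)^20.

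For p = 10%: 0.90^20 = 0.122, 0.925^20 = 0.210 and 0.95^20 = 0.358 for f = 100%, 75% and 50%.

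| p | f = 100% | f = 75% | f = 50% |
|---|---|---|---|
| 5% | 1.0 expected; none 36% | 0.75; 47% | 0.5; 60% |
| 10% | 2.0; 12% | 1.5; 21% | 1.0; 36% |
| 20% | 4.0; 1.2% | 3.0; 3.9% | 2.0; 12% |

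Even with complete recording, 0 of 20 leaves an upper 95% limit of 1 − 0.05^(1/20) = 13.9% (one-sided) or 1 − 0.025^(1/20) = 16.8% (two-sided). These limits assume that every case is recorded.

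**3. Effect of closer watching in 7.1**

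Assume 25% of patients are at higher risk with a 30% rate, and the rest have a 10% rate. The true expectation is 20 × (0.25 × 0.30 + 0.75 × 0.10) = 3.0 cases. With 50% recorded in everyone, the expectation is 1.5. With 100% recorded in the higher-risk group and 50% in the rest, it is 20 × (0.25 × 0.30 + 0.75 × 0.05) = 2.25.

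Closer watching of one group raises the total. What it distorts is the comparison between groups: the recorded rates become 30% against 5%, a ratio of 6, where the true ratio is 30 / 10 = 3.

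**The case against.** The strongest reply is that section 8 lists the kinds of effect to record and does not impose a test of cause. It does not confine recording to those effects in so many words, and it mentions no decision by staff. Section 8 also speaks of any incident, and 7.1 has all participants monitored. Annex 7 takes dizziness and headache straight from the patient. Patients are seated and supervised, so a fall during a session would be seen. The video procedure in 5.2 collects feedback at the end of the session. Safety is not a stated objective of this 20-patient acceptability pilot.

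Much of this stands. A reader might infer that all harms are filtered by unmasked staff and that the study will under-count them. The documents do not support that. An exclusive rule and a staff judgement are inferences from the wording. Annex 7 bypasses staff for several symptoms. Lack of masking adds little where there are no arms to compare, although staff expectations could still affect the absolute count. A reader might also blame the extra attention to higher-risk patients in 7.1 for under-counting, but it works the other way, and 5.7 plans no comparison of event rates between patient types.

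The gap remains. The promise about incidents is a duty to inform the company, with no definition, question or data entry behind it. Monitoring in 7.1 is supervision during care. Neither creates an all-cause record or a question put to every patient.

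**Conclusion.** The point holds in a limited form. Harm recording is unsystematic: the stated duty depends on a link with VR, nothing provides for all-cause recording, no fixed question is asked, and 5.7 names no analysis of side effects. Annex 7 is a real but partial safeguard, and its timing is contradictory.

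Under-counting is a credible risk that the documents neither establish nor quantify. At an assumed 10% true rate, the chance of an empty section 8 record runs from 12% with full recording to 36% with half recorded. No source supports any particular recording share, and capture through Annex 7 would reduce the effect for the symptoms it covers. The defect does not touch the main acceptability analysis. It should be corrected because the change is cheap and a low count could not otherwise be interpreted.

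**What to change.** - **Section 8:** record every new or worsened symptom, fall or other untoward event, in every patient, from the start of session 1 to the final visit, whatever its presumed cause. Enter the judged relation to VR in a separate field.
- **Asking:** put one fixed question to every patient at each session, worded to cover that session and the time since the last one. State in 7.1 that all patients get the same question, whatever extra watchfulness their care calls for. Answers given before a patient withdraws are then already on record.
- **Section 5.7:** report the number of patients with at least one event out of all who start session 1, first for all causes and then for VR-related events, with exact confidence intervals.
- **Sections 5.4.1, 5.5 and 6.1:** reconcile when the questionnaires are given.

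Cost: wording, a line on the data template and a little staff time. One question at each of 8 sessions for 20 patients is at most 8 × 20 = 160 short enquiries, by staff who already accompany the sessions. Some unrelated events will be listed. Answers about the time between sessions depend on recall by patients with cognitive impairment. Effects that begin after the final visit stay outside the window.

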9. DISSEMINATION AND COMMUNICATION PLANS OF RESULTS

Our goal is to share the findings of this study on the use of virtual reality in cognitive decline with the scientific and medical community. Consequently, we intend to try to publish the results of this study in a peer-reviewed scientific journal and, to the extent possible, present them at a relevant conference or conference in the field. While we cannot guarantee acceptance on such platforms, we are committed to transparency and ethics, and we we will strive for making our findings widely accessible.

10. SOURCE OF FINANCING

This study benefits from a grant from the AMB, which is intended for the creation of digital content from Reality Telling, the company in charge of developing the virtual reality program. As recipients of this scholarship, Reality Telling assumes the responsibility of coordinating the procurement of all hardware equipment necessary for the sessions. This includes organizing and securing resources to obtain virtual reality glasses, tablets, bags, modems and SIM cards for Internet connection, if necessary.

In addition, Reality Telling guarantees the necessary training for the efficient use of these technological tools in the context of research. This support eliminates any significant additional costs associated with the development and implementation of the virtual reality program.

BSA professionals, within the framework of their regular responsibilities, will conduct the investigation. While this involves time commitment to study design, data collection and analysis, and preparation of results for publication, these costs are part of BSA's regular operations and do not require additional funding.

Additional costs may be associated with publishing study results. Should these arise, we will seek additional funding through other available scholarships or grants. If such financing is not obtained, these costs will be assumed by BSA. In this way, we ensure that both the financing and the resources necessary to carry out and disseminate the study are duly guaranteed.

11. WORK PLAN FOR CONDUCTING THE STUDY

Phase 1 (July-September 2023): Definition and validation of the beneficiaries, formulation of the study protocol and initial development of the VR exercises. Milestone 1: Formulation of the study protocol, assessment and approval by the BSA research committees and the GTP CEIC (July-September 2023) Milestone 2: Start of development of VR exercises (July-August 2023)

Phase 2 (September-November 2023): Completion of the development of the VR exercises, recruitment of patients who will participate in the study and training of the CSSC Day Hospital staff for the implementation of the immersive VR experiences. Preparation for the start of data collection.

Milestone 3: Completion of the development of VR exercises (September-October 2023) Milestone 4: Patient recruitment (September-October 2023) Milestone 5: Training of Day Hospital staff for the implementation of immersive VR experiences (September-October 2023) Milestone 6: Preparation for the start of data collection (November 2023) Milestone 7: Start of data collection: November 2023

Phase 3 (November-December 2023): Implementation of the pilot study with selected patients and data collection. Completion of data collection at the end of this period. Milestone 8: Start of the pilot study (November 2023) Milestone 9: Completion of the pilot study and data collection (December 2023)

End of data collection: December 2023 - January 2024 Interim reports of results (if applicable): Not applicable in this study due to its short duration.

Final report: January 2024

Milestone 10: Preparation of the final report (January 2024) Milestone 11: Presentation of the final report that includes the results of the pilot study, analysis of the data collected, conclusions and recommendations for future research or implementations based on VR experiences (January 2024)

Phase	Milestone	Chronology
Phase 1	Milestone 1: Formulation of the study protocol, assessment and approval by the BSA research committees and the GTP CEIC	July-Septem ber 2023
August-September 2023	Milestone 2: Start of development of VR exercises	July-August 2023
Phase 2:	Milestone 3: Completion of VR exercises development	September October 2023

September-Novem ber 2023	Milestone 4: Patient recruitment	September October 2023	
	Milestone 5: Training of Day Hospital staff for the implementation of immersive VR experiences	September October 2023	
	Milestone 6: Preparation for the start of data collection	November 2023	
	Milestone 7: Start of data collection	November 2023	
Phase 3:	Milestone 8: Start of the pilot study	November 2023	
November-Decem ber 2023	Milestone 9: Completion of the pilot study and data collection	December 2023- January 2024	
Final Report:	Milestone 10: Preparation of the final report	January 2024	
January 2024	Milestone 11: Presentation of the final report	January 2024	

